### 6.3.6 End of Study and Follow-up

- Participants will be instructed to contact study staff and make them aware of any adverse events that occur during the study (severe hypoglycemia, diabetic ketoacidosis, etc). Information about adverse events will also be asked at each study follow up visit.
- Upon completion of the clamp procedures, participants will be instructed to monitor their glucose levels carefully and contact clinic staff if they note that

insulin adjustments are needed. Follow up appointments with a diabetes care provider will be recommended within 2 weeks of the end of the study. Their primary diabetes provider will also be contacted and made aware that they have completed the study.

- If participants withdraw from the study early, participants will be instructed to monitor their glucose levels carefully and contact clinic staff if they note that insulin adjustments are needed. Follow up appointments with a diabetes care provider will be recommended within 2 weeks of ending the study. Their primary diabetes provider will also be contacted and made aware that they have withdrawn from the study.
- Diabetes providers will be made aware of any adverse events that take place during the study or information that is considered medically necessary for their overall health. Participants will be made aware of any information that may be shared with their diabetes provider. There is no plan to share results with the primary diabetes providers unless something pertinent to their diabetes management occurs during the study.

**6.3.7 Removal of subjects:** Participants may be withdrawn if they are unable to follow the dietary requirements and study procedures, including keeping a diet journal, testing ketone levels, and wearing a CGM at least 75% of the time.

## 6.4 Statistical Method

**6.4.1 Statistical Design:** see below.

### 6.4.2 Sample Size Considerations

For all aims, we base our sample size on the unadjusted comparison of paired means, which is a conservative approach. Therefore, given that our statistical analyses will be based on adjusted models and models that specifically take into account within-person correlation in outcomes of interest, we should be sufficiently powered to answer our research questions.

Aim 1: The goal time in range in adolescents with T1D 60% +/- 10% of their time in the target range of 70-180 mg/dL but based on our preliminary work in this population we expect that the mean percent of time in range is around 50-55%. With 16 eligible subjects, we will have 80% power at the two-sided alpha of 0.05 to detect a minimum increase in the expected mean by 7.5% (from 50-55% on standard carbohydrate diet to 57.5-62.5% on low carbohydrate diet - an increase of 1.5 hours per day - an effect size of  $7.5\% \div 10\% = 0.75$ ), using a paired-sample t-test. If we assume 20% attrition, we will need 20 individuals for the study.

Aim 2: Using data from a previously published study, where changes in glucagon levels during 2-step euglycemic-hypoglycemic clamp in youth with T1D were assessed over a period of 1 year(15), we anticipate that with 16 subjects (n=20 with 20% attrition, see aim 1) we will have 80% power at the two-sided alpha of 0.05 to detect a between-diet change in mean glucagon levels of at least 9.5 pg/mL (standard deviation=12.5 pg/mL, effect size of  $9.5 \text{ pg/mL} / 12.5 \text{ pg/mL} = 0.75$ ), using a paired t-test. We will also report the incremental rise and area under the curve (AUC) as well as mean and peak glucagon levels.

Aim 3: Using estimates of variability (standard deviations [sd]=5 during euglycemia and sd=10 during hypoglycemia) from a previous study, with 16 subjects (20 subjects with 20% attrition) we will have 80% power at the two-sided alpha of 0.05 to detect an effect size in the range of 0.75-1.0, using a paired t-test, meaning that when on low carbohydrate diet, subject

will have on average higher awareness of hypoglycemia (e.g., at least 5-10 point difference in the mean total score) than when on standard diet. For interviews, following qualitative description methodology, data will be coded, and emerging patterns will be combined into descriptive themes. Thematic data analysis will proceed concurrently with data collection. Any differences in coding among researchers will be discussed until resolution is achieved. Emerging themes will be examined within and across interviews. Data coding and analysis will be conducted concurrently with ongoing data collection until emerging patterns and themes. Analyses will be conducted using a consensus model approach. All analytic decisions will be recorded in research memos or detailed notes of observations during data collection. The rationale for coding decisions and conceptual or theoretical issues that emerge during data analysis will be kept so as to maintain an audit trail during the data collection through the process of analysis. The research team has experience in qualitative methods and thematic analysis and those less experienced have received adequate training prior.

## 6.5 Planned Analyses

### 6.5.1 Primary Objective Analysis

- **Statistical Analyses Aim 1:** The unadjusted between-diet-group comparison of the primary endpoint, percent time in the target range of 70-180 mg/dL during the 2nd week of each diet, will be performed using a two-sided paired t-test. The adjusted analysis will be performed using linear mixed effects (LME) modeling, with a random intercept for each subject, diet effect, and adjusting for a participant's age, BMI and duration of diabetes. The mean adjusted between diet-group difference in percent time in the target range will be reported, along with the surrounding 95% confidence intervals based on 500 bootstrapped samples (2.5th percentile and 97.5th percentile of the distribution). Secondary outcomes, including time spent with hypoglycemia (<54 mg/dL, <70 mg/dL) and hyperglycemia (>180 mg/dL, >250 mg/dL), average sensor glucose level, will be analyzed similarly to the primary outcome. The proportion of days with elevated fasting  $\beta$ -hydroxybutyrate levels ( $\geq 0.6$  mmol/L) during each diet period will be compared using paired-proportions z-test in the unadjusted analysis and using generalized linear mixed effects (GLMM) modeling (a random intercept, link=logit for the binary outcome yes/no elevated levels with Bernoulli distribution) with covariates of age, BMI, and duration of diabetes. GLMM will also be utilized in the comparison of the number of episodes of diabetic ketoacidosis and severe hypoglycemic events during each period (a random intercept, link=log for a count outcome with Poisson distribution). Statistical analyses for all aims will be implemented using R and SAS 9.4 (Cary, NC) statistical software. Statistical significance will be established at the two-sided alpha of 0.05.

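### Section 6.5.1 gives the primary endpoint two analyses at one 5% threshold without naming the deciding one; if the percentile bootstrap interval decides, the false-positive rate at 16 pairs is about 8%

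*Combined protocol and SAP*

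**What the plan says.** In section 6.5.1, "The unadjusted between-diet-group comparison of the primary endpoint" (percent time in 70-180 mg/dL in the second week of each diet) is by a two-sided paired t-test. The text continues: "The adjusted analysis will be performed using linear mixed effects (LME) modeling, with a random intercept for each subject, diet effect", with age, BMI and diabetes duration as covariates. The adjusted diet difference is to be reported with a 95% interval taken from the 2.5th and 97.5th percentiles of 500 bootstrap samples. The Aim 1 text ends: "Statistical significance will be established at the two-sided alpha of 0.05". Neither analysis is called primary, deciding, supportive or a sensitivity analysis.

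Section 6.4.2 bases the sample size on the unadjusted paired comparison. "With 16 eligible subjects", it says, "we will have 80% power at the two-sided alpha of 0.05 to detect a minimum increase in the expected mean by 7.5" percentage points, and "If we assume 20% attrition, we will need 20 individuals for the study". It calls the unadjusted basis conservative, "given that our statistical analyses will be based on adjusted models and models that specifically take into account within-person correlation".

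Section 6.5.9 excludes participants with less than 75% CGM wear from the analysis. It does not distinguish the two analyses, and it does not mention participants with usable data from only one diet period.

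**The concern.** The conclusion of a trial of about 16 pairs can turn on which procedure is read. The trial is unblinded (section 6.1.4 marks blinding as not applicable), so a rule left open can be settled after both results are known. One rule that the text permits, the paired t-test, holds its 5% level. Another, checking whether the percentile bootstrap interval excludes zero, does not hold it at this sample size. Leaving the rule unnamed therefore leaves the trial's actual error rate undefined, and a borderline result could be presented as positive on one rule when it is not positive on the other.

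**Working it through.** **Inputs from the documents.** Two-sided 5% level (6.5.1). From 6.4.2: 16 evaluable pairs, a 7.5-point difference, 20% attrition and 20 enrolled. The SD of 10 comes from the statement "The goal time in range in adolescents with T1D 60% +/- 10% of their time in the target range of 70-180 mg/dL"; the plan's effect size of 7.5/10 = 0.75 uses it as the SD of the paired difference. From 6.5.1: 500 bootstrap samples, percentile limits.

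**Assumptions, not in the documents.** Normal data; no period effect; bootstrap resampling by participant; covariates measured once per participant; a missing period missing at random; within-person correlation of 0.2, 0.5 or 0.8 with the SD of the difference held at 10.

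**1. The plan's own figure.** The noncentrality is 0.75 × √16 = 3.0 with 15 degrees of freedom. The noncentral t gives power of 80.06%, and 16 is the smallest n that reaches 80%. Inflation for attrition: 16/(1 − 0.20) = 20. Both stated figures reproduce.

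**2. Size of the percentile interval, by formula.** With complete pairs and participant-level covariates, the mixed-model diet estimate equals the mean paired difference. The bootstrap standard error of that mean is smaller than the usual one by √((n−1)/n), and the percentile limits sit at about ±1.96 of it. The false-positive rate is therefore about P(|t with n−1 df| > 1.96 × √((n−1)/n)).

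- n = 16: 1.96 × √(15/16) = 1.898, giving 7.7%.
- n = 20: 1.96 × √(19/20) = 1.910, giving 7.1%.

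The t-test's critical value at n = 16 is 2.131. With an SD of 10 the standard error is 10/√16 = 2.5, so the half-widths are 1.898 × 2.5 = 4.7 points and 2.131 × 2.5 = 5.3 points. An observed difference between these two values is significant on one rule and not on the other.

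**3. Simulation with no diet effect.** 20,004 trials per row; Monte Carlo standard error about 0.2 points. The mixed model was fitted by REML with three covariates. Figures are percentages of trials declared positive.

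| Complete pairs + one-period participants (correlation) | Paired t | Bootstrap interval | Mixed model, t-based | Paired t or bootstrap | Paired t or t-based model |
|---|---|---|---|---|---|
| 16 + 0 (0.5) | 4.75 | 7.93 | 4.71 | 7.95 | 4.88 |
| 20 + 0 (0.5) | 5.05 | 7.68 | 5.05 | 7.72 | 5.21 |
| 16 + 2 (0.5) | 5.04 | 7.90 | 5.00 | 8.05 | 5.70 |
| 16 + 4 (0.2) | 5.10 | 7.77 | 5.16 | 8.23 | 6.29 |
| 16 + 4 (0.5) | 5.10 | 7.69 | 5.17 | 8.08 | 6.02 |
| 16 + 4 (0.8) | 5.10 | 7.88 | 5.15 | 8.03 | 5.79 |

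**4. Where the excess comes from.** The bootstrap interval alone gives 7.7 to 7.9%. Also counting a positive t-test adds 0.02 to 0.04 points with complete pairs and 0.15 to 0.46 points with one-period participants.

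**5. Disagreement at the design effect.** In a separate run of 20,000 trials with 16 complete pairs and a true difference of 7.5 points, the t-test was positive in 80.5% and the bootstrap interval in 86.5%. The verdicts were opposite in 6.1%; a further check put this at about 6 to 7%.

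**The case against.** The strongest reply is that the plan already leans one way. Section 6.4.2 reads coherently as a simple, conservative power calculation for analyses that will be adjusted, and 6.5.1 attaches a reported estimate and interval only to the adjusted difference. That is fair: 6.4.2 does not contradict 6.5.1. But the sentence is a power argument covering all aims. It is not a rule for declaring the primary result, so the gap remains.

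Three stronger readings are tempting, and the documents do not support them.

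- A reader might infer that two tests at 5% push the error to 9% or so. For two independent tests it would be 1 − 0.95² = 9.75%. These two are nearly the same statistic, the simulated rate never exceeded 8.2%, and the second look contributes at most about half a point.
- A reader might infer that the plan decides from the bootstrap interval. It says only that the interval will be reported, and sets the significance level in a separate sentence. A model-based test with the interval as description is an equally natural reading, and under it the 8% disappears.
- A reader might infer that the two analyses use different participants. The plan neither states nor excludes this. Four one-period participants would require all of the assumed attrition to come from people with usable data on exactly one diet; anyone lost earlier contributes to neither analysis.

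**Conclusion.** The point holds in a limited form. The deciding analysis for the primary endpoint is not named, and the permitted rules do not have the same error rate: about 5% for the paired t-test or a t-based mixed-model test, and about 8% at 16 pairs if significance is read from the percentile bootstrap interval. The excess is a small-sample fault of that interval, not chiefly a multiplicity problem. Without the bootstrap rule, the chance that either analysis is positive is about 5% with complete pairs and about 6% if four one-period participants enter the mixed model.

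The figures rest on the assumptions listed with the working. The equality of the two estimates needs complete pairs and a single BMI value per participant; the plan also records BMI at both clamp visits and does not say which value enters the model. The change should be made, but it does not call the design or the sample size into question.

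**What to change.** Add to section 6.5.1: *The primary conclusion rests on the diet effect from the linear mixed model, tested at two-sided 0.05 with a small-sample t-based test and matching 95% CI, including all participants with evaluable CGM data in at least one period. The paired t-test on complete pairs and the percentile bootstrap interval are supportive and do not change the conclusion.*

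The t-based wording is essential. Naming the mixed model while leaving the percentile interval able to decide would keep the error rate at 7.7 to 7.9%; with the t-based test it is 4.7 to 5.2%.

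Naming the paired t-test as the deciding analysis is equally valid: 5% error and 80.1% power at 16 pairs, as 6.4.2 computes.

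The cost is two sentences, with no new data and no change in sample size. The option of quoting the other analysis as primary is given up, and the deciding interval is slightly wider (half-width 5.3 instead of 4.7 points at 16 complete pairs with an SD of 10). Section 6.4.2 needs no change if the mixed model is named.

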### 6.1 Treatment

#### 6.1.1 Identity of Investigational Product – N/A

#### 6.1.2 Dosage, Administration, Schedule

Visit 1 will consist of informed consent and enrollment. The study will begin with a 1 to 3 -week baseline period for insulin optimization. At visit 2, participants will be randomized for either the very low carbohydrate diet or standard carbohydrate diet that they will follow for 2 weeks. At visit 2 (virtual/telephone/in person), participants will be instructed on how to keep diet journal and report relative amounts of food during the 24-hour recall phone calls. After 2 weeks on the first diet, participants will come to the HRU/CSRU/Masonicare for Visit 3, the hyperinsulinemic euglycemic-hypoglycemic clamp. Following this visit, the participants will have a 1-3 week washout period. At Visit 4 (virtual/telephone/in person), the next diet will be reviewed. They will follow that diet for 2 weeks and then return to the HRU/CSRU/Masonicare for Visit 5 and the second hyperinsulinemic euglycemic-hypoglycemic clamp. After this visit, the study will be complete.

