**Figure 1. Schedule of visits during the study.**

#### 6.1.3 Method of Assignment/Randomization

Block randomization will be used to ensure an equal number of participants complete diets in each of the specified sequences.

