### 6.2.2 Safety and Pregnancy-related policy

- Women of childbearing age will have a urine pregnancy test performed at the time of the screening/enrollment visit and the need for contraception for the entire duration of the study will be discussed. Additional urine pregnancy tests will take place the morning prior to each clamp visit (visit 3 and visit 5).
- Hematocrit levels will be tested prior to the clamp procedures (visit 3 and visit 5). Samples will be obtained with the minimum necessary blood volume. The point of care YSI glucose determinations require only 0.3 ml of blood per measurement. We will ensure that blood volume obtained does not exceed a maximum of 5cc/kg in pediatric participants and 550 ml in adult participants
- Continuous glucose monitoring data will be reviewed twice per week (or more frequently as needed) to ensure participants are wearing the devices and to monitor for hyperglycemia and hypoglycemia. Insulin doses will be titrated by trained research staff based on clinical care standards to ensure safety by minimizing hypo- and hyperglycemia.
- Daily fasting blood ketone checks will be performed during the study intervention and as needed for symptoms of ketosis. If ketones are elevated, participants will be instructed to call the diabetes emergency line 24/7 for further instruction. All patients in our clinics are instructed to call this number if they develop elevated ketones at home. These values will also be reviewed 3 times per week when 24-hour dietary recall is performed.

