**Follow Up Calls:**

- Participants will be followed up weekly to make insulin dose adjustments during the insulin optimization and washout periods. Insulin pump and CGM information will be reviewed during these phone calls.
- Participants will also be screened for any symptoms that may be related to very low carbohydrate diets on a weekly basis or more often as needed (symptoms including nausea, vomiting, abdominal pain, constipation, fatigue, and lightheadedness). If these occur, participants will be instructed to ensure adequate caloric intake is achieved and hydration is maintained.

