#### 6.5.5 Interim Analysis (if applicable) – N/A

#### 6.5.6 Health economic evaluation – N/A

#### 6.5.7 Other - N/A

6.5.8 **Subsets and Covariates** - confounding variables include of age, BMI, and duration of diabetes. Details of the plan to evaluate confounding variables are above in Statistical Aim 1.

6.5.9 **Handling of Missing Data** – Participants that are unable to wear their CGM for at least 75% of the time will be excluded from the analysis.

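### The Aim 1 crossover analysis has no period term, and the coverage of its bootstrap 95% interval depends on an unstated resampling unit

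*Combined protocol and SAP*

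**What the plan says.** Section 6.1.2 describes a two-period crossover: "At visit 2, participants will be randomized for either the very low carbohydrate diet or standard carbohydrate diet", then a washout and the other diet. Section 6.1.3 adds: "Block randomization will be used to ensure an equal number of participants complete diets in each of the specified sequences".

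Section 6.5.1 analyses percent time in range in two ways. The unadjusted comparison is a two-sided paired t-test. The adjusted one is given as "linear mixed effects (LME) modeling, with a random intercept for each subject, diet effect, and adjusting for a"; three covariates are then named, namely age, BMI and diabetes duration. The adjusted difference is reported with a 95% interval "based on 500 bootstrapped samples (2.5th percentile and 97.5th percentile of the distribution". The unit that is resampled is not given, and the section does not say which of the two results governs. Section 6.5.8 repeats the covariates: "confounding variables include of age, BMI, and duration of diabetes". No section adds period or sequence.

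Three statements bear on drift between periods. Section 6.1.2 says "The study will begin with a 1 to 3 -week baseline period for insulin optimization". The follow-up calls in section 6.3.5 say "Participants will be followed up weekly to make insulin dose adjustments during the insulin optimization and washout periods". Section 6.2.2 says "Insulin doses will be titrated by trained research staff based on clinical care standards".

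Section 6.4.2 sizes Aim 1 on a paired t-test: 16 evaluable participants, a 7.5-point difference, SD 10, 80% power, and 20 enrolled to allow for 20% attrition.

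**The concern.** In a two-period crossover, anything that changes between the first and second period enters each within-person difference with a sign set by the sequence. If period is not fitted, that change is counted as noise. If the two sequences finish with unequal numbers, part of it also moves the diet estimate. The optimisation phase and washout may limit drift, but insulin continues to be titrated, so drift cannot be ruled out. Blocking balances allocation; it cannot guarantee equal completion. Dropout and the 75% CGM-wear exclusion in section 6.5.9 both act after randomisation.

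The interval is a separate matter. Percentile limits from a small sample contain no t correction. Resampling participants also loses the n/(n−1) variance correction. Resampling observations within each diet instead breaks the pairing and can make the interval far too wide. The section permits either reading. At stake are the stated confidence level of the main effect estimate and the possibility that the interval and the t-test disagree on the same endpoint.

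**Working it through.** **Inputs.** From section 6.4.2: n = 16, difference 7.5 points, SD of the within-person difference 10 (the reading under which the stated effect size of 0.75 fits a paired t-test), two-sided alpha 0.05. Assumed: normal differences, and period effects of 0 to 7.5 points, since the documents give no size.

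**1. The plan's own figure.** Noncentrality is 0.75 × √16 = 3.0 on 15 df, so exact power is 80.06%. Also 16/(1 − 0.20) = 20. Both figures reproduce.

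**2. Interval, participants resampled, no period effect.** With complete pairs, the mixed-model diet coefficient equals the mean paired difference (7.752 for both in a simulated check). The percentile half-width is about 1.96 × √(15/16) = 1.898 standard errors; t on 15 df needs 2.131. The closed form P(|t₁₅| ≤ 1.898) gives 92.3%. Simulation with 500 resamples gives:

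- percentile interval: 91.8% to 91.9% coverage, mean width 9.2 points
- t-interval: about 95% coverage, mean width 10.5 points
- parametric bootstrap from the fitted model: 92.8% coverage

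In about 3% of null trials the participant-resampled interval excludes zero while the t-test does not reject.

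**3. Interval, rows resampled within diet.** The bootstrap then ignores the within-person correlation ρ. With equal variances, the half-width in true standard errors is about 1.96 × √[(15/16)/(1 − ρ)]: 1.90 at ρ = 0, 2.27 at 0.3, 2.68 at 0.5 and 3.46 at 0.7. Simulated coverage in one run was 92.3%, 96.9%, 98.3% and 99.8%. A second run gave 93.3%, 96.4%, 98.8% and 99.7%.

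**4. Period term, power at 8/8.** A period effect π shifts each difference by +π or −π according to sequence. Without a period term, the expected sample variance is 100 + π² × 16/15, so at π = 5 the apparent SD is √126.7 = 11.3. Type I error in the last three columns is for the planned t-test.

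| Period effect (points) | Power, planned t-test, 8/8 | Power, period fitted, 8/8 | Type I, 8/8 | Type I, 9/7 | Type I, 10/6 |
|---|---|---|---|---|---|
| 0 | 80.2% | about 80% | 5.0% | 5.0% | 5.0% |
| 2.5 | 78.0% | about 80% | 4.3% | 4.5% | 5.1% |
| 5 | 72.2% | about 80% | 2.9% | 3.4% | 4.9% |
| 7.5 | 62.4% | about 80% | 1.5% | 2.2% | 4.5% |

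**5. Unequal completion.** The estimate shifts by π × (n₁ − n₂)/16: 2/16 = 0.125π at 9/7 and 4/16 = 0.25π at 10/6. At π = 5 that is 0.63 and 1.25 points, with direction set by which sequence lost more. If 20 are randomised 10/10 and four are lost at random:

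- P(8/8) = 45²/4845 = 0.418
- P(9/7) = 2 × 10 × 120/4845 = 0.495
- P(10/6) = 2 × 210/4845 = 0.087

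Unequal completion then has probability 1 − 0.418 = 58%. If two or three of the four losses come before randomisation it is 47%, and if all four do it is 0%. These two figures assume allocation as equal as possible.

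**6. The defects interact.** An omitted period effect widens the participant-resampled interval. At π = 5 its coverage rises to between 94.4% and 94.8%. Fitting period but keeping percentile limits leaves coverage at about 91% to 92%.

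**The case against.** The strongest reply is that the planned test is sound and the rest is conditional. Much of this stands.

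- A reader might infer that omitting period invalidates the primary test or biases the diet effect. The calculations do not support that. The paired t-test holds its level at about 5% or below in every split examined. The shift under unequal completion averages to zero if losses are random.
- A reader might infer that the plan's interval covers 92%. That holds only if participants are resampled, or nearly so with a parametric bootstrap. Section 6.5.1 does not say so, and another reading makes the interval too wide.
- The two defects do not reach full size together. A small period effect leaves the undercoverage but little power to recover; a large one does the reverse.
- The period effect sizes are assumptions. The largest, 7.5 points, equals the whole target difference, and at 2.5 points the loss is about 2 points of power.
- Section 5.4 speaks of 20 participants to complete the study. With 20 completers, power is 89%, or about 83% with an omitted 5-point period effect. Participant-resampled coverage is still only about 92%.

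A reader might also infer that covariate adjustment can never alter the diet estimate. That is true in general only for complete pairs with covariates fixed per person. Section 6.3.5 measures weight and BMI again at visits 3 and 5, and section 6.5.1 does not say which BMI enters the model. Under the fixed-covariate reading, age, BMI and duration generally leave the estimate and its standard error unchanged. They then do not support the statement in section 6.4.2 that sizing on the unadjusted comparison is conservative.

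What the reply does not remove is that the reported interval has no determinate coverage, and that the design, at 80.06% power with 16 completers, has no margin to absorb avoidable noise.

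**Conclusion.** The point holds in two parts, and it should be fixed.

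First, the nominal 95% interval for the adjusted Aim 1 effect depends on an unstated choice. With 16 normal pairs and little or no period effect, coverage is about 92% with participant resampling and about 93% to 99.8% with row resampling within diet, for correlations from 0 to 0.7. This needs no assumption about drift beyond its being small.

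Second, omitting period is a loss of efficiency. At 8/8 it costs about 2, 8 and 18 points of power for assumed period effects of 2.5, 5 and 7.5 points. Unequal completion adds a shift of 0.125 or 0.25 times the period effect in the realised estimate.

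Neither part makes the planned t-test invalid. The calculations cover Aim 1 only. Section 6.5.2 mentions bootstrapped intervals for Aim 2 without a method or resample count, so these coverage figures should not be carried over.

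**What to change.** In section 6.5.1, add period as a fixed effect to the Aim 1 mixed model, keeping the random intercept. Report the diet effect with a t-based 95% interval (Kenward-Roger, about 14 df). In simulation the period-adjusted t-interval covers about 95%, and power stays at about 80% at 8/8 whatever the period effect. If a bootstrap is kept, make it a studentised sensitivity analysis that resamples participants, and state the unit. Make both changes together, because adding period alone does not repair the percentile interval.

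State which BMI measurement enters the model. If covariates are fixed per person, remove covariate adjustment as a reason for calling the Aim 1 sample size conservative. A period term in the Aim 2 and Aim 3 between-diet comparisons is suggested for consistency only; its effect there was not calculated.

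The cost is SAP wording and one degree of freedom. If there is no period effect, exact period-adjusted power is 79.7% at 8/8, 79.0% at 9/7 and 77.1% at 10/6, against 80.06% planned: losses of about 0.4, 1 and 3 points. The interval becomes about 14% wider than the participant-resampled percentile interval (10.5/9.2 = 1.14). Participants, visits and enrolment are unaffected.
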